## 2. Specific Aims and Objectives

**1. To test the effect of a single t-PBM session on cerebral blood flow (CBF), while irradiating R-dlPFC, in subjects with impulsivity due to BD**

*Hypothesis:* a single t-PBM session on the R-dlPFC will significantly increase BOLD-signal at the R-dlPFC, relative to sham.

**2. To test the effect of repeated t-PBM sessions on CBF, after irradiating R-dlPFC, in subjects with impulsivity due to BD**

*Hypothesis:* repeated t-PBM sessions on the R-dlPFC will significantly increase BOLD-signal at the R-dlPFC at day 5 relative to baseline.

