### **3. General Description of Study Design**

This is a single-blind study to test the neuropsychological and clinical effects of t-PBM with NIR in BD. For our primary aim of examining the effect of tPBM on CBF, the study is additionally sham-controlled. Twenty patients with a diagnosis of bipolar disorder, not currently in a depressive, manic, or mixed state episode, will undergo one sham and one NIR- t-PBM session on day 1 (within MRI scanner), and one daily NIR- t-PBM session from day 2 to 5. On day 5, the NIR t-PBM session will also occur in the MRI scanner. The fMRI scan will measure BOLD changes during sham t-PBM (day 1) and during NIR t-PBM (day 1 & 5), on R-dlPFC.

Impulsivity will be assessed by the BIS at pre-screen (for inclusion criteria), baseline, treatment day 5, and the follow-up visit; and by the gambling tasks at baseline, after the first NIR t-PBM (day 1), after the fifth NIR t-PBM (day 5), and at the follow-up visit. Other aspects of impulsivity and executive functioning will be assessed by the I-7 and BRIEF-A at baseline, day 5, and the follow-up visit. The MOODS-SR-Last Week will be administered at baseline, day 5, and the follow-up visit to assess change in mood, particularly hypomanic symptoms. At screening, subjects will complete the MOODS-SR Lifetime.

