### *Baseline Visit*

Adverse events, as well as concomitant medications and therapies, will be collected. Participants will complete the Young Mania Rating Scale (YMRS), the BIS, the BRIEF-A, the I-7, the CAST-IRR, and the SAFTEE. A licensed clinician will administer the C-SSRS and the CGI-S. Skin color will be recorded using the NIS-SCS. Participants will complete two computerized gambling tasks: The Iowa gambling task and the Delgado gambling task. The order of administration of the gambling tasks will be randomized. This appointment will last approximately 90 minutes.

*Treatment 1*

Vitals will be assessed and recorded. The MRI Safety Checklist will be completed and signed before the MRI. Participants will undergo an MRI Scan. While in the scanner, participants will first undergo a structural scan and resting state scan, followed by a functional scan during which the participants will receive a sham t-PBM treatment. This scan will be followed by a pre-stimulation resting-state functional acquisition. At this time, active t-PBM will be administered, immediately followed by a post-stimulation resting state scan. Participants will then complete the Delgado gambling task. A functional sequence will be collected during the administration of the gambling task. Finally, participants will undergo a post-stimulation resting state functional scan. The MRI will last approximately 75 minutes in total.

Participants will know that they are receiving both active and sham treatment, but they will not be told in which order the treatments will be delivered. Participants will complete the PBQ, CAST-IRR, TSRQ, and the Iowa Gambling Task at the conclusion of the visit. Study staff will complete an intervention tracking form.

*Treatments 2-4*

Treatments 2, 3, and 4 should ideally occur once daily during the three days following the first treatment administration. If necessary, this window can be extended so that these three treatment visits occur within ten days of the Baseline/Treatment 1 visit (in this case, the timing of follow up visits will be adjusted accordingly). Adverse events and concomitant medications and therapies will be assessed and recorded at each visit. Participants will complete the TSRQ and CAST-IRR after treatment administration. Study staff will complete an intervention tracking form for each study visit.

*Treatment 5*

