Treatment 5 should ideally occur the day after Treatment 4. If necessary, this window can be extended so that this visit occurs within ten days of the Treatment 1 visit (in this case, the timing of follow up visits will be adjusted accordingly). Adverse events, concomitant medications and therapies, and vitals will be assessed and recorded. The MRI Safety Checklist will be completed and signed before the MRI. Participants will complete the MOODS-SR, the BIS, the BRIEF-A, and the I-7.

Participants will undergo an MRI Scan. A structural scan and a pre-stimulation resting state functional scan will be collected first. Active t-PBM will be administered immediately after the resting-state scan, followed by a post-stimulation resting state functional scan. Participants will then complete the Delgado gambling task. A functional sequence will be collected during the gambling task administration. The MRI will last approximately 45 minutes in total.

Participants will complete the SAFTEE, the CAST-IRR, the TSRQ, and the Iowa gambling task after the MRI/t-PBM session. Study staff will complete an intervention tracking form.

*Clinical Check-in Call*

A licensed study clinician will call the participant (phone or video call) approximately 2-3 days after the final treatment session. Adverse events and concomitant medications and therapies will be assessed and recorded. The clinician will administer the C-SSRS and the CGI-S/I. The clinician may use the PHQ-9 and/or ASRM to guide their call with the study participant, though these scales do not need to be completed in full. The purpose of this call is to check in on the general safety and well-being of the participant.

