## 9. Statistical Analysis

Preprocessing of MRI and fMRI data will be performed with the FreeSurfer software package, scripted in Bash. Slice-time correction, motion-correction, and co-registration of functional BOLD scans, Time of Repetition (TR), and participant will then be performed. BOLD signals will then be smoothed to a full-width half maximum (FWHM) of 3mm and z-scored at every voxel.

t-PBM related increase of BOLD percent signal change (PSC) averaged across all ROI voxels will be assessed during the first scanning session where the participant receives both sham and NIR over the R-dlPFC. PSC of t-PBM related increase in BOLD both during and after stimulation will be the dependent variable with the independent variable being the condition of t-PBM during the first session (sham vs. NIR).

BOLD signal will again be assessed during the 5th NIR session as a PSC across all ROI voxels in comparison with the BOLD PSC from the first NIR session to observe any BOLD changes after 5 NIR treatment sessions. The dependent variable will be the BOLD signal and the independent variable will be the timepoint: day 1 vs. after 5 sessions (day 5).

For both gambling tasks, the gambling task net gain score will be analyzed for changes from baseline to after treatment on day 1, baseline vs day 5, and baseline vs follow up. The BIS, BRIEF-A, and I-7 will be analyzed for changes from baseline to day 5 and follow up. Here, the dependent variable will be the gambling tasks' net gain scores, BIS, BRIEF-A, and I-7 total score. The independent variable is the timepoint baseline vs. day 5 (for the gambling tasks) and follow up. The MOOD-SR will also be analyzed for a decrease in impulsivity at each timepoint of baseline vs. day 5 and follow up. A General Mixed Models Regression will be used with time as a fixed effect and subject as a random effect.

Secondary analyses will also be performed for the BIS, BRIEF-A, I-7, MOOD-SR, SAFTEE, and TSRQ. Each scale and their respective subscales will be analyzed for specific changes at

each timepoint to better understand the effect t-PBM NIR has on the symptoms and presentation of BD. These additional analyses will also be helpful in assessing the initial safety profile of t-PBM in this psychiatric population.

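### The visit procedures name a BOLD run during sham but none during active t-PBM, which conflicts with the during-and-after outcome planned for Aim 1

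*Combined protocol and SAP*

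**What the plan says.** Three parts of the protocol require BOLD data while the light is on.

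- Section 2 words Aim 1 as follows: "To test the effect of a single t-PBM session on cerebral blood flow (CBF), while irradiating R-dlPFC".
- Section 3 states: "The fMRI scan will measure BOLD changes during sham t-PBM (day 1) and during NIR t-PBM (day 1 & 5), on R-dlPFC".
- Section 9 defines the Aim 1 outcome: "PSC of t-PBM related increase in BOLD both during and after stimulation will be the dependent variable". The independent variable is condition (sham or NIR) in the first session.

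The scan order is given visit by visit in section 6. On day 1 (Treatment 1), a structural and a resting-state scan come first, "followed by a functional scan during which the participants will receive a sham t-PBM treatment". The next step is: "This scan will be followed by a pre-stimulation resting-state functional acquisition". For the active session the text then reads: "At this time, active t-PBM will be administered, immediately followed by a post-stimulation resting state scan". The Delgado task with a functional sequence follows, and a further post-stimulation resting run closes the scan.

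On day 5 (Treatment 5) a structural scan and a pre-stimulation resting run come first. Then: "Active t-PBM will be administered immediately after the resting-state scan, followed by a post-stimulation resting state functional scan". The Delgado task with a functional sequence comes last.

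For Aim 2, section 9 takes the PSC of the fifth NIR session "in comparison with the BOLD PSC from the first NIR session".

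**The concern.** The section 6 text describes sham and NIR differently. Sham is delivered inside a named functional run. Active t-PBM is described as a step between two resting runs, with no acquisition attached to it. A scanner operator working from that text would record BOLD during sham and not during NIR.

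Aim 1 is the only aim with a sham comparator and the only one with a power statement (20 matched pairs, section 9). Its outcome has a during part and an after part. BOLD that is not recorded during the exposure cannot be reconstructed, so a misreading of the procedure would remove the during part of the comparison for every participant scanned that way.

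The after part has a different difficulty. The resting runs following sham and following NIR are not equal in number or role, and section 9 does not say which of them enter the contrast.

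**Working it through.** The plan gives no figure on this point, so the check is a comparison of texts.

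**Step 1. Runs required.** Sections 2, 3 and 9 together require a during-sham run on day 1, a during-NIR run on day 1, a during-NIR run on day 5, and an after-stimulation measurement for sham and for NIR on day 1.

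**Step 2. Runs named in section 6.**

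| Delivery | Run before | Run during | Resting run(s) after |
|---|---|---|---|
| Sham, day 1 | resting state | functional run named | one, labelled pre-stimulation (for NIR) |
| NIR, day 1 | the same pre-stimulation run | none named | two: one immediate, one after the Delgado task |
| NIR, day 5 | pre-stimulation resting | none named | one |

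A task-based functional run during the Delgado task is also listed after NIR on both days. No such run follows sham.

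**Step 3. Compare.** A during run is named for 1 of 1 sham deliveries and for 0 of 2 active in-scanner deliveries. Section 3 requires it for all three.

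**Step 4. Is this only loose wording?** Section 6 does state concurrency where it applies: for sham, and for the gambling task on both days. Only active t-PBM is written as a sequence, at both MRI visits. The MRI Scanning text in section 6 lists structural, resting-state and task-based sequences but ties none to stimulation, so it does not fill the gap.

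**Step 5. Consequence by aim, if section 6 is followed literally.**

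- Aim 1, during part: sham has data and NIR has none, so the contrast cannot be formed.
- Aim 1, after part: a resting run follows each condition, so a contrast can be formed, but it is not defined. The run after sham is also the run before NIR. NIR has two candidates, and the later one follows a gambling task that has no counterpart after sham. The first run after each condition is therefore the closest match.
- Aim 2: day 5 has no sham and plays no part in Aim 1. A during-stimulation value for day 1 versus day 5 would be missing. Pre- and post-stimulation resting runs are listed on both days, so a post-stimulation comparison remains possible.

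**Step 6. Time needed.** Table 1 gives an exposure of 333 s, which is 333 / 60 = 5.55 minutes. On days 1 and 5 this already takes place in the scanner.

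**The case against.** The strongest reply is that the acquisition is plainly planned. Section 3 says so for both days, section 2 frames Aim 1 around the period of irradiation, and section 9 builds the outcome on it. Section 1 reports that delivering t-PBM in the scanner while recording BOLD has already been shown feasible. Section 6 is silent on a during-NIR run and does not exclude one. The MRI Scanning text also refers to imaging protocols validated at the imaging center, which are not part of these documents and may specify the run.

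Most of this stands. A reader might infer that during-NIR data will be absent for all 20 participants. The documents do not support that: it would follow only if the visit text overrode sections 2, 3 and 9, and nothing says it does.

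What the reply does not remove is the contradiction. Stated intent in the design section does not help if the step-by-step procedure leaves the run out, and that procedure names the corresponding run for sham.

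**Conclusion.** The point holds as an internal inconsistency. Section 6 (Treatment 1 and Treatment 5) must be reconciled with sections 2, 3 and 9. Its size is conditional: if the visit text is followed as written, the during part of the Aim 1 contrast is lost; if scanning follows section 3, nothing is lost and only the text is wrong. The documents do not settle which will happen.

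The undefined after contrast is a second, smaller gap and does not depend on that condition.

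Three further inferences are tempting and should not be drawn.

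- That Aim 2 fails. Section 2 words Aim 2 in terms of flow after irradiation, and the reference in section 9 to the fifth session can mean the visit rather than the exposure. Post-stimulation data are listed on both days.
- That sham has only during data and NIR only after data. A resting run does follow sham.
- That the shared run between sham and NIR costs a calculable amount of precision. This would require the contrast to be a difference of two pre-to-post changes, and section 9 never specifies that estimator.

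**What to change.** 1. In the Treatment 1 and Treatment 5 procedures, state that a functional BOLD run is acquired during active t-PBM, with the same sequence and length as the sham run.
2. In section 9, name the runs that form each Aim 1 contrast. For the during contrast, use the sham run and the matched day 1 NIR run. For the after contrast, use the first run after each condition, and acknowledge that the run after sham is also the one before NIR.
3. If no during-NIR run is in fact acquired, restrict the Aim 1 outcome to post-stimulation PSC and bring sections 2 and 3 into line.

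The cost is a sentence in each visit procedure and a short definition in section 9. Recording during an exposure that already takes place in the scanner should add no exposure time. The change should be made before further scans are acquired, because a missed run cannot be recovered.

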### *Screening*

Subjects will review the consent form with the study clinician (PI or Co-I; MDs) and be given the opportunity to ask questions. Consent will be obtained by a licensed physician investigator. If the screening visit is conducted remotely using Zoom, the consent form will be collected electronically using REDCap following the MGH eConsent Template. Subjects will then receive an electronic copy of the consent form through their provided email which they can download and keep for their records. This is an automatic function of REDCap. If the screening visit is conducted in-person, the consent form may be collected on REDCap or on paper. If the consent form is signed on paper, subjects will receive a paper copy of the consent. Subjects will be considered enrolled in the study once they sign the consent form.

Subjects will be asked a series of questionnaires to assess eligibility for the study, including the Mini International Neuropsychiatric Interview (MINI), and the Columbia Suicide Severity Rating Scale (C-SSRS). Demographic information, concomitant medications and therapies, prior treatment history, and medical history will be collected. Subjects will complete an MRI Screening Form and the MOODS-SR Lifetime. Screening will also include a dipstick toxicology urinalysis and, if applicable, a dipstick pregnancy test. If the subject is eligible, they will be invited to continue to the baseline visit. If not eligible, the subject will not be invited to continue with the study.

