This 161-item self-report scale assesses manic-depressive symptoms. Participants are asked to answer “Yes” or “No” to each question. Subdomains measure Moods, Energy, Cognition, and Rhythmicity. Time frame is either lifetime or the last week, depending on scale used.

*MRI Safety Checklist*

This form identifies risk factors that may make MRI participation unsafe.

*New Immigrant Survey-Skin Color Scale (NIS-SCS)*

The NIS-SCS is an 11-point scale, ranging from zero to 10, with zero representing albinism, or the total absence of color, and 10 representing the darkest possible skin. The ten shades of skin color corresponding to the points 1 to 10 on the Massey and Martin Skin Color Scale are depicted in a chart, with each point represented by a hand, of identical form, but differing in color. The respondent never sees the chart. We gather this data for use as a potential covariate in analyses as skin color can affect absorption of NIR.

*Patient Health Questionnaire (PHQ-9)*

This nine-item self-report measure assesses the presence and severity of depressive symptoms over the past 14 days. This scale will be administered as part of the pre-screening phase.

*Perceived Blinding Questionnaire (PBQ)*

The PBQ is a self-report questionnaire to determine the degree to which the participant believes they are receiving active treatment or sham.

*Prior Treatment Log*

This form captures information regarding prior treatments for bipolar disorder or other mental health concerns.

*Systematic Assessment for Treatment Emergent Events (SAFTEE)*

The SAFTEE is a commonly used instrument originally developed by NIMH and adapted into a self-report instrument. The version of the scale that we plan to use is the same used by the multi-center, NIMH-sponsored CO-MED trial, and it examines in a systematic fashion all possible treatment-emergent side effects and probes specific adverse symptoms, including suicidal thoughts and behaviors, and self-injurious behavior.

*t-PBM Self-Report Questionnaire (TSRQ)*

An open-ended questionnaire focusing on potential inconveniences and discomforts from the t-PBM treatment.

*Young Mania Rating Scale (YMRS)*

This 11-item clinician-rated scale is used to assess the presence and severity of manic symptoms.

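### The Section 6 Baseline Visit list omits the last-week MOODS-SR that both Aim 4 contrasts need; a smaller point is that the planned day-5 form looks back over 2 to 3 days before any active treatment

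*Combined protocol and SAP*

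**What the plan says.** Aim 4 in Section 2 predicts a lower MOODS-SR total at day 5 and at follow-up, each against baseline. Section 3 names the version and the visits: "The MOODS-SR-Last Week will be administered at baseline, day 5, and the follow-up visit to assess change in mood, particularly hypomanic symptoms". Section 9 analyses both contrasts in a mixed model with a fixed time effect and a random subject effect. It ranks neither contrast and describes no term for days since Treatment 1.

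Section 6 sets out what is done at each visit. At Screening: "Subjects will complete an MRI Screening Form and the MOODS-SR Lifetime". At the Baseline Visit the questionnaire list reads: "Participants will complete the Young Mania Rating Scale (YMRS), the BIS, the BRIEF-A, the I-7, the CAST-IRR, and the SAFTEE". The clinician ratings, skin colour record and two gambling tasks follow, with no MOODS-SR. The Treatment 1 procedures do not name it either. At Treatment 5: "Participants will complete the MOODS-SR, the BIS, the BRIEF-A, and the I-7". That sentence stands ahead of the scan and the fifth active session. The form appears again at the Follow Up Visit, about a week after session 5.

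On recall, the assessment description states: "Time frame is either lifetime or the last week, depending on scale used". Items are answered yes or no.

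On timing: "Treatments 2, 3, and 4 should ideally occur once daily during the three days following the first treatment administration" and "Treatment 5 should ideally occur the day after Treatment 4". The permitted extension is: "If necessary, this window can be extended so that this visit occurs within ten days of the Treatment 1 visit".

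**The concern.** There are two separate points, of unequal weight.

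**Baseline score.** Both Aim 4 contrasts subtract a last-week score taken before treatment. The overview in Section 3 promises that score, but the visit procedures do not collect it. Coordinators usually run a visit from its procedure list. If they do so here, the only pre-treatment MOODS-SR is a Lifetime form, which covers a different period and cannot stand in for a last-week score. Once the first active session has been given, a pre-treatment last-week score cannot be obtained.

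**Day-5 recall week.** A seven-day look-back from a visit four days after the first active session reaches into untreated days. If symptoms on those days influence the answers, the day-5 change is pulled towards zero. The pull is greatest when the schedule is kept and disappears when the visit is late enough, yet Section 9 treats all these visits as one timepoint. A null day-5 result could then be taken as evidence against Aim 4 when part of the recall week had no treatment in it.

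**Working it through.** **1. Where a MOODS-SR is named**

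| Place | MOODS-SR |
|---|---|
| Section 3 | Lifetime at screening; Last Week at baseline, day 5 and follow-up |
| Section 6, Pre-Screen | none |
| Section 6, Screening | Lifetime |
| Section 6, Baseline Visit | none |
| Section 6, Treatment 1 | none |
| Section 6, Treatments 2-4 | none |
| Section 6, Treatment 5 | yes (version not named) |
| Section 6, Follow Up Visit | yes (version not named) |

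Section 3 and Section 6 agree at screening, Treatment 5 and follow-up. They disagree only at baseline, the one score that both Aim 4 contrasts share.

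**2. Timing of the day-5 form**

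Let T1 be the day of Treatment 1, which is the first active session and is day 1 in Section 3. Treatments 2 to 4 fall on T1+1, T1+2 and T1+3, and Treatment 5 on T1+3+1 = T1+4. Day 1 + 4 = day 5, so the plan's own label is reproduced. The latest permitted visit is T1+10.

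**3. Recall days before any active treatment**

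Let s be the number of days from T1 to the Treatment 5 visit, and count the day of T1 as treated.

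- If the recall week is the seven days before the visit day: max(0, 7 - s).
- If the visit day is one of the seven: max(0, 6 - s).

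| Treatment 5 visit | Seven days before the visit day | Visit day counted |
|---|---|---|
| T1+4 (planned) | 7 - 4 = 3 (43%) | 6 - 4 = 2 (29%) |
| T1+5 | 7 - 5 = 2 (29%) | 6 - 5 = 1 (14%) |
| T1+6 | 7 - 6 = 1 (14%) | 0 |
| T1+7 to T1+10 | 0 | 0 |

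As listed, the form precedes the fifth session, so at T1+4 it reflects four sessions.

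**4. The same count at follow-up**

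Follow-up is about s + 7 days after T1, from 4 + 7 = T1+11 to 10 + 7 = T1+17. Pre-treatment recall days are max(0, 7 - 11) = 0 at the earliest. The word about does not matter here: even a visit three days after session 5 would be at T1+4+3 = T1+7, and the count would still be 0.

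**The case against.** **On the baseline score.** Section 3 schedules the last-week form at baseline, and Aim 4 and Section 9 depend on it, so the intention is plain. A reader might infer that the trial collects no last-week baseline score. The documents do not support that; they contradict each other, and the loss occurs only if Section 6 is followed without Section 3. What stands is that the operational list is the one that is wrong, and that an omission at that visit cannot be repaired.

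**On the day-5 recall week.** Aim 4 is the last of four aims. Power is stated only for Aim 1, and sham control applies only to the blood-flow aim. The unaffected follow-up contrast is already planned, and with time as a fixed effect the two contrasts can be estimated separately. All of this stands and keeps the point small.

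**On ranking follow-up first.** A reader might infer that follow-up should become the main Aim 4 contrast. Its recall week runs from the day of session 5 to six days later, or starts the day after session 5 if the visit day counts. It holds at most one treatment day, so it mainly measures persistence, and an effect that fades over several days would be diluted there too. The documents give no ground for preferring persistence to response during the course, so reporting both is defensible.

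**On the size of the dilution.** It is tempting to say that the planned day-5 contrast shows 4/7 = 57% of the effect. That needs every recall day to count equally and the effect to be complete from session 1. The documents give no rule for how long a symptom must be present to be answered yes, and Aim 4 concerns repeated sessions. They also do not say how often visits will be rescheduled. No percentage of effect lost can be defended.

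**Conclusion.** The baseline mismatch is an error as written. If Section 6 is followed, neither Aim 4 contrast can be computed; if Section 3 is followed, both can. This rests only on comparing the two sections.

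The day-5 point holds as a limitation on interpretation. Between 2 and 3 of 7 recall days precede active treatment on the planned schedule, falling to 0 from T1+7. The range reflects only whether the visit day is counted. Any resulting bias is towards no effect; recall overlap gives no reason to expect a false benefit. Its size is unknown and varies with rescheduling.

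The finding does not reach the blood-flow aims. It also should not be extended to, or declared absent from, the BIS, BRIEF-A and I-7: the documents give no recall period for those scales. The window extension is not itself a fault, because later visits have fewer pre-treatment recall days.

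**What to change.** 1. **Section 6, Baseline Visit:** add the MOODS-SR Last Week to the questionnaire list so that it matches Section 3. The cost is some added time for a 161-item form at a visit estimated at 90 minutes, unless that estimate already allows for it.

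2. **Section 9:** add two or three sentences. Report the day-5 MOODS-SR contrast together with each participant's days since Treatment 1. State that its recall week can include days before the first active session, so a null day-5 result is not by itself evidence against Aim 4. State that follow-up is the contrast whose recall week lies wholly after the first active session. This needs no new visit, participant or measure, and the visit windows can stay as they are.

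Ranking follow-up above day 5 is optional. If it is done, Section 9 should say that the main question then becomes persistence after the course.

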#### *Follow Up Visit*

The follow up visit takes place approximately one week after the final treatment session. This visit will be completed in person. Adverse events and concomitant medications and therapies will be assessed and recorded. Participants will complete the MOODS-SR, the BIS, the BRIEF-A, the I-7, the SAFTEE, the Delgado gambling task, and Iowa gambling task. The order of administration of the gambling tasks will be randomized. A licensed clinician will administer the C-SSRS and the CGI-S/I.

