*Suicidality Standard Operating Plan (SOP):* If a subject spontaneously expresses suicidal ideation and the thoughts are passive, vague, or infrequent, the study team will respond with close monitoring of the subject. This may include phone calls, video calls, or in-person check-ins between the study clinician and the subject. If the suicidal ideation includes more specific thoughts, intent, and/or plans, if the subject responds “Yes” to questions 4 or 5 of the C-SSRS, or if the subject answers 1, 2, or 3 to Question 9 of the PHQ-9, then they will be proactively discontinued from the study and referred to adequate care.

*Risks associated with study tasks:* Performing tasks can result in frustration related to difficulty with performance, or boredom during longer sittings. Participants may refuse to answer questions that make them uncomfortable.

*Risks of Magnetic Resonance Imaging:* MRIs use powerful magnets to make images. There are no known radiation risks associated with MRI. However, individuals with metal implants, such as surgical clips or pacemakers, should not have an MRI. All credit cards and other items with magnetic strips should also be kept out of the MRI room. People who feel uncomfortable in confined spaces (claustrophobia) may feel uncomfortable in the narrow tube. The MRI makes loud banging noises as it takes images. Earplugs can be used to reduce the noises. The MRI can be stopped at any time at subject’s request. If the study subject is or suspects they are pregnant, they should not participate in this study. Study staff will assess chance of pregnancy. If there is any uncertainty, a study physician can recommend a pregnancy test. The MRI has the potential, during normal routine use, to cause localized warming of participant’s skin and of the underlying tissues. The participant will be instructed to immediately inform study staff if they experience discomfort due to warming and the procedure will be stopped.

Some people experience dizziness or rarely nausea when going into an MRI scanner and these sensations may be more common in scans with higher magnetic fields. In most cases, these symptoms only last a short time. However, some people may experience them throughout the scan and/or continue to experience them for a short period of time after (generally, less than half an hour). No case of permanent problems is known.

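### The only SAFTEE taken during treatment follows an MRI scan, so its change from baseline cannot separate t-PBM symptoms from scanner symptoms

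*Combined protocol and SAP*

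**What the plan says.** Section 6 schedules the SAFTEE three times.

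- **Baseline Visit:** "Participants will complete the Young Mania Rating Scale (YMRS), the BIS, the BRIEF-A, the I-7, the CAST-IRR, and the SAFTEE". No MRI is listed.
- **Treatment 5:** "Participants will complete the SAFTEE, the CAST-IRR, the TSRQ, and the Iowa gambling task after the MRI/t-PBM session". Of the scan at that visit the protocol says: "The MRI will last approximately 45 minutes in total". Active t-PBM is delivered during it.
- **Follow Up Visit,** about a week after the last session: "Participants will complete the MOODS-SR, the BIS, the BRIEF-A, the I-7, the SAFTEE, the Delgado gambling task, and Iowa gambling task". No MRI is listed.

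The SAFTEE is absent from the other treatment visits. After the Treatment 1 scan, which contains both sham and active t-PBM: "Participants will complete the PBQ, CAST-IRR, TSRQ, and the Iowa Gambling Task at the conclusion of the visit". After Treatments 2-4, which Section 3 places outside the scanner: "Participants will complete the TSRQ and CAST-IRR after treatment administration".

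Section 9 lists the SAFTEE and the TSRQ among the secondary analyses, looks at change at each time point to understand what t-PBM does, and adds: "These additional analyses will also be helpful in assessing the initial safety profile of t-PBM in this psychiatric population".

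On MRI itself, Section 7 says: "Some people experience dizziness or rarely nausea when going into an MRI scanner". It adds that such symptoms can outlast the scan for a short while, usually under 30 minutes, and that MRI can warm the skin and the tissue beneath it.

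**The concern.** A checklist that is meant to show what a device does should be filled in at least once when the device has been used and the main competing cause of symptoms is absent. Here the one rating during treatment comes at a visit where participants have also had a scan of about 45 minutes. Some symptoms that Section 7 assigns to MRI resemble those it assigns to t-PBM: warmth and discomfort appear under both.

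At stake is the reading of the SAFTEE part of the safety profile in bipolar disorder. A rise from baseline to Treatment 5 would be reported under t-PBM although part of it may come from the scanner. The primary BOLD comparison is not affected.

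**Working it through.** The plan states no figure on this point, so the check sets the visit schedule against the analysis text.

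**Step 1: exposure at each SAFTEE (Section 6, with Section 3 for which sessions are in the scanner)**

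| Visit | Active t-PBM | MRI | SAFTEE |
|---|---|---|---|
| Baseline | no | none listed | yes |
| Treatment 1 | yes (and sham) | yes | no |
| Treatments 2-4 | yes | none listed | no |
| Treatment 5 | yes | yes | yes |
| Follow-up | no | none listed | yes |

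The Treatments 2-4 text once runs the baseline and Treatment 1 visits together. Even if they fall on one day, the SAFTEE is listed with the baseline procedures and not with those that close the scan visit.

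**Step 2: what the contrast estimates.** Let τ be the symptom change due to t-PBM, μ the change due to MRI, and δ any drift over time or expectation effect. Then:

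- Baseline to Treatment 5 = τ + μ + δ.
- Across the three SAFTEE ratings, the indicators for t-PBM and MRI are identical: (0,0), (1,1), (0,0). No model fitted to these ratings can estimate τ and μ separately.

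**Step 3: does this depend on the recall period?** The SAFTEE description in Section 6 gives none. With a long window, the follow-up form could reach back to the Treatment 5 session, but it would then cover that session's scan and its t-PBM together. Confounding at Treatment 5 holds under any window. Only the amount of scanner carry-over changes.

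**Step 4: how large could it be?** The documents give no per-participant rate of scanner symptoms. For illustration only, take 20 participants, no t-PBM effect, and an assumed share p with a new scanner symptom on the Treatment 5 form. Expected reports = 20p, and P(at least one) = 1 − (1 − p)^20.

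| p (assumed) | Expected reports | P(at least one) |
|---|---|---|
| 0.05 | 1 | 0.64 |
| 0.10 | 2 | 0.88 |
| 0.20 | 4 | 0.99 |
| 0.30 | 6 | >0.99 |

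These rows show sensitivity to p. They do not estimate the problem, and Step 2 does not need them.

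**Step 5: what an added Treatment 4 rating gives.** Its indicators are (t-PBM 1, MRI 0), so baseline to Treatment 4 = τ + δ, free of μ if the recall window leaves out the Treatment 1 scan. On the ideal daily schedule Treatment 4 falls three days after that scan (day 1 to day 4), so a window of a week would include it and a window back to the previous visit would not. The drift term δ remains, because sham control applies only to the cerebral blood flow aim (Section 3).

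**The case against.** The strongest case against has five parts.

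- **Other data exist.** The TSRQ is completed and adverse events are recorded at each of Treatments 2-4, and Section 9 names the TSRQ beside the SAFTEE. This stands, and it limits the point. A reader might infer that the side-effect profile cannot be assigned to the device at all; the documents do not support that. What remains is that the TSRQ is open-ended and the SAFTEE is the form described as systematic, so neither source repairs the SAFTEE contrast.
- **Scanner symptoms are brief.** Section 7 says so of dizziness and nausea, and Section 6 says only that the SAFTEE comes after the session, without fixing the delay or the order relative to the Iowa task. It would be wrong to read this as immediately after. The effect may be small, but it is uncontrolled.
- **The earlier study proves nothing.** In the TRIADE table (Section 6), five events are named for MRI: discomfort 2, panic attack 1, anxiety 1, mental fog 1. Their relatedness codes are 5, 3, 4, 1 and 4, so four of five are possibly related or higher by the printed key. A reader might infer that misattribution has already happened. The codes are ratings of single events and not SAFTEE scores, no denominator is given, one other row carries a 0 that is outside the key, and Section 1 describes a depression study at the same institution with t-PBM delivered inside the scanner. A rating of related is therefore not shown to be wrong.
- **Over-counting is the cautious direction for safety.** True, but it still blurs which symptoms belong to the device.
- **The comparison is uncontrolled anyway.** Also true. The added rating removes one known competing cause and leaves the others.

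**Conclusion.** The point holds in a limited form. The baseline-to-Treatment 5 SAFTEE change combines t-PBM and MRI symptoms, and the three scheduled ratings cannot separate them. This follows from the visit schedule and needs no assumed rate. That this contrast is planned rests on reading Section 9's change at each time point to include baseline versus Treatment 5, as it does explicitly for the other scales.

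Its size is one secondary safety instrument at one visit. How many reports are affected cannot be worked out from the documents: any count out of 20 depends wholly on an assumed rate. The benefit of the fix depends on a SAFTEE recall period that the documents do not state. This is a cheap improvement to a planned safety analysis and not a threat to the trial's main aim.

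**What to change.** - **Section 6, Treatments 2-4:** add the self-report SAFTEE after Treatment 4.
- **Section 6, SAFTEE description:** state a recall window that excludes the Treatment 1 scan, for example since the previous visit, and use the same window at Treatment 5. State the window for baseline and follow-up too, since a reach-back to the previous visit may be longer there.
- **Section 9:** report the baseline-to-Treatment 4 SAFTEE change, together with the TSRQ and adverse-event data from Treatments 2-4, as the profile of t-PBM without MRI. Report the Treatment 5 SAFTEE as combined MRI plus t-PBM symptoms. Describe both as uncontrolled pre-post changes.

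The cost is one more form at an existing visit, a few minutes per participant, and a few sentences in the protocol. The MRI-free contrast covers only the sessions before the fifth. The Treatment 4 to Treatment 5 difference should not be read as a clean MRI effect, because it also contains whatever the fifth session adds.
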